Epidural Morphine for Geriatrics Undergoing Lower Abdominal Cancer Surgery: A Dose-Response Study

Clinical Study Protocol

By

[name] ^{1,*} [MBBCh],

February 2020

Resident of anesthesia, ICU and pain management

Supervised by

[name] ¹ [MD], [name] ² [MD], and [name] ¹ [MD]

Affiliations:

1. Department of anaesthesiology, South Egypt Cancer Institute, Assiut University, Assiut, Egypt.

2. Department of anaesthesiology, Faculty of Medicine, Assiut University, Assiut, Egypt.

***Corresponding author at:** Assiut University, Faculty of Medicine, [name].

E-mail: [contact]

Conflict of interests: the authors have no conflicts of interest.

Fund: local departmental fund without receiving any external grant.

Ethical approval: IRB of Assiut University Faculty of Medicine, No: 17101147.

NCT number: NCT04316871

Background

Acute postoperative pain is a common complaint for several days after surgery (1). However, acute postoperative pain remains even more under controlled in elderly patients, especially those with cognitive impairment and malignancy (2,3). Geriatric population is reported to be at higher risk for unwanted side effects from analgesic treatments compared to younger patients due to different major risk factors such as: decline in organ function, polypharmacy, pharmacokinetics, drug sensitivity, and frailty (4). Despite of the higher risk of opioids, especially morphine, causing toxicity and adverse effect; they are still the cornerstone treatment of severe acute postoperative pain (5). Morphine in those patients is very likely to cause toxicity because of accumulation of its active metabolites compared to other opioids with fewer or no active metabolites (6). Epidural morphine is an effective route for an effective drug.(7,8) Furthermore, unwanted side effects with neuraxial opioids are minor and managed easily.(9) Regarding clinical outcomes, clinical studies showed a lot of improvements associated with postoperative opioid analgesia (10–12). Now, there is a clinical necessity to achieve the best management of acute postoperative pain in elderly patients with the least possibility of adverse side effects. We aim in this randomized, assessor blinded, clinical trial at Assuit University to determine the optimum dose of epidural morphine for the highest control of acute postoperative pain in geriatrics who are planned to have lower abdominal cancer surgery.

Aim of the research

Our primary outcome is total patient-controlled analgesia (PCA) morphine sulphate (MS) consumption within seventy-two hours after surgery. Secondary outcomes include pain-intensity, measured using visual analog scale (VAS), Ramsay sedation scale (RSS), and nausea, vomiting and pruritus scale. Each of all the previous outcomes is to be recorded at 2, 8, 16, 24, 36, 48 and 72 hours after surgery.

Research Methods and Procedures

- 1- Study Design: randomized, assessor blinded, clinical trial.
- 2- Study Setting: Assuit University Hospitals, Anaesthesia and ICU department.
- 3- Study subjects:

A) Inclusion criteria:

Eligible patients are men and women aged ≥ 60 years, who are planned to undergo lower abdominal cancer surgery. Surgeries via infra-umbilical abdominal incision are considered eligible such as ovary, bladder, and colorectal surgeries.

B) Exclusion criteria:

We excluded patients with contraindications to neuraxial analgesia. The absolute contraindications are lack of consent from the patient, elevated intracranial pressure (ICP), primarily due to intracranial mass and infection at the site of the procedure (risk of meningitis). While the relative contraindications are (13,14):

- Pre-existing neurological diseases (particularly those that wax and wane, e.g., multiple sclerosis).

- Severe dehydration (hypovolemia), due to the risk of hypotension. The risk factors for hypotension include hypovolemia, age greater than 40 to 50 years, emergency surgery, obesity, chronic alcohol consumption, and chronic hypertension.
- Severe mitral and aortic stenosis and left ventricular outflow obstruction as seen with hypertrophic obstructive cardiomyopathy.
- Thrombocytopenia or coagulopathy (especially with epidural anaesthesia, due to the risk of epidural hematoma. Of note about coagulopathy, the placement of neuraxial block requires reevaluation. The American Society of Regional Anaesthesia (ASRA) publishes updated guidelines that detail timing for neuraxial anaesthesia for patients on oral anticoagulants, anti-platelets, thrombolytic therapy, unfractionated, and low molecular weight heparin. Review the latest guidelines before proceeding with the procedure.

C) Groups:

Patients were randomized (by using a table of random numbers) to one of four groups to receive a single dose of epidural preservative-free morphine out of four doses: 0 mg (group D); 1.5 mg (Group A); 3mg (Group B) and 4.5 mg (Group D) at the beginning of surgery. A total volume of 10 mL was injected; 5 mL of bupivacaine hydrochloride 0.125% with the previously mentioned study doses of preservative-free morphine diluted in 5 mL preservative-free normal saline by the hospital pharmacist.

D) Sample Size Calculation:

The sample size will be calculated using G* Power software 3.1.9.2 considering a study power of 80% and a significance level of 0.05 to detect an effect size of 0.75 using one-

way ANOVA test/t-test. Assuming total IV-PCA morphine consumption is the main outcome variable, and the maximum total IV-PCA morphine consumption was 12 ± 16 mg while in healthy controls was 70 ± 35 mg according to previous studies (15-17), the estimated minimum required sample size, after assuming 33% dropouts, will be 88 patients (22 patients in each group).

Statistical Analysis Plan

Data will be analyzed using IBM SPSS statistics version 24 for Windows 10. A value of $P < 0.05$ was considered significant. The data will be tested for normality using the Shapiro–Wilk test. Normally distributed variables such as age and BMI are presented as the means \pm SDs and will be compared with ANOVA. When the assumption of normality was rejected, the nonparametric Kruskal–Wallis test for independent samples will be used for comparison. Significant Kruskal–Wallis test values will be Bonferroni corrected when various time points are investigated and when multiple tests are applied. For data presented as counts and percentages, a chi-squared test will be applied.

Procedure

A standardised epidural catheter insertion protocol will be followed in all the study groups. A 20-gauge, open-tip epidural catheter will be inserted into the T9-10 interspace and advanced 5 cm into the epidural space while patients are in the sitting position. A total volume of 10 mL will be injected; 5 mL of 0.125% bupivacaine hydrochloride was mixed with each of the study doses and diluted in 5 mL of preservative-free normal saline by the hospital pharmacist. We will not use

the test dose of 0.5% lidocaine or 1:200000% epinephrine and will only use Dogilotti's principle for confirmation of correct epidural catheter placement. If there are no rapid onset within 1-2 minutes of neuraxial sensory block, which will be observed only during the intrathecal delivery of the local anaesthetic, the placement of the epidural catheter will be activated. After 30 min, the sensory block around the level of T8-T10 will be tested by pinprick. The diluted preservative-free epidural morphine studied doses will be identical in appearance to be unrecognizable, so neither the patient nor the attending anaesthesiologist could identify the administered dose. General anaesthesia will be then induced using 2 mg/kg propofol and 2 mcg/kg fentanyl. Endotracheal intubation will be performed with rocuronium (0.5 mg/kg), and general anaesthesia will be maintained with sevoflurane and rocuronium (0.2 mg/kg on demand). Heart rate and mean arterial blood pressure (MAP) will be kept within 20% of the preoperative baseline values as determined by the attending anaesthesiologist. Ondansetron (4 mg) will be given as an antiemetic at skin closure. At the end of the surgery, muscle relaxation will be reversed by treatment with 0.05 mg/kg neostigmine and 0.01 mg/kg atropine. After extubation, the patients will be admitted to the post-anaesthesia care unit (PACU) until they are fully recovered from anaesthesia.

Thereafter, the patients will be transferred to the ICU, and a standardised close monitoring will be performed for 72 hours to detect early or late respiratory depression. The same doses of epidural morphine for each patient will be administered at 24 hr and 48 hr postoperatively.

Strength points and Limitations

The main strengths of this study are that it is highly reproducible and addresses the daily clinical aspects of epidural morphine in older adults. However, this study is limited by its focus on lower abdominal cancer surgeries only; additionally, it is a single centre study focused on unimodal analgesia. Therefore, the generalizability of our results is limited. All other systemic analgesics are as under-researched as epidural morphine in this age group. Therefore, further studies with larger sample on other drugs and on different types of surgeries are needed to tailor adequate multimodal pain management protocols with the least risk to the older adults. The study is also limited to clinical response and pharmacodynamics of epidural morphine in the older adults and did not investigate the pharmacokinetics, which should be examined in future studies. Due to the vulnerability of older adults, we included only ASA I and II patients to assess the balancing dose of epidural morphine versus age only. The relationship between the dose of epidural morphine and common comorbidities in this age group should also be investigated.

References:

2. Connelly P. The management of chronic pain in older persons. Vol. 46, *Journal of the American Geriatrics Society*. Blackwell Publishing Inc.; 1998. p. 635–51.
3. Schofield PA. The assessment and management of peri-operative pain in older adults. Vol. 69, *Anaesthesia*. 2014. p. 54–60.
4. Popp B P tenoy R. Management of chronic pain in the elderly: pharmacology of opioids and other analgesic drugs. In: In: IASP TF on P in the E, Ferrell B, Ferrell BA E, editors. *Pain in the elderly : a report of the Task Force on Pain in the Elderly of the International Association for the Study of Pain*. Seattle (WA): IASP Press; 1996. p. 21–4.
5. McKeown JL. Pain Management Issues for the Geriatric Surgical Patient. Vol. 33, *Anesthesiology Clinics*. W.B. Saunders; 2015. p. 563–76.

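### Does printing the letter D for both the 0 mg and the 4.5 mg arm leave the control and highest-dose groups indistinguishable?

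*Combined protocol and SAP*

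**What the plan says.** The arms are defined once, in Research Methods and Procedures, item 3, subsection C) Groups. Patients are randomised "to one of four groups to receive a single dose of epidural preservative-free morphine out of four doses", and the arms are then listed as "0 mg (group D); 1.5 mg (Group A); 3mg (Group B) and 4.5 mg (Group D) at the beginning of surgery".

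Three other places bear on the point:

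- D) Sample Size Calculation gives the total: it "will be 88 patients (22 patients in each group").
- Procedure describes the blinding. The hospital pharmacist dilutes the doses, which are "identical in appearance to be unrecognizable, so neither the patient nor the attending anaesthesiologist could identify the administered dose".
- Procedure also says: "The same doses of epidural morphine for each patient will be administered at 24 hr and 48 hr postoperatively".

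None of these three places uses a group letter. The Statistical Analysis Plan compares groups by ANOVA, Kruskal–Wallis or chi-squared tests and names no arm by letter either.

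**The concern.** A key from arm codes to treatments should be one-to-one, and this one is not. The sentence in C) Groups is the only place where letters and doses are paired, and by letter alone the control and the top dose cannot be told apart. These two arms form the widest contrast in a dose-response study, so confusing them would do more damage than confusing two neighbouring doses.

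The setting adds to the worry. The preparations look alike, so a mix-up could not be seen at the bedside, and identification depends on records. Procedure also has each patient's own dose given again at 24 and 48 hours, so a misread code could carry forward. If the allocation list, the preparation record or the dataset used the printed letters, a record marked D could not be checked against the protocol, and a result reported for Group D could belong to either end of the dose range.

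**Working it through.** No published figure needs reproducing. The check is a count of labels, followed by a search for any step that depends on them.

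**1. Count the labels (C) Groups).**

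| Dose | Printed letter |
|---|---|
| 0 mg | D |
| 1.5 mg | A |
| 3 mg | B |
| 4.5 mg | D |

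There are 4 dose–letter pairs and 4 distinct doses, but only 3 distinct letters (A, B, D). D occurs twice and C does not occur.

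**2. Confirm that four arms are intended (D) Sample Size Calculation).** 88 / 22 = 4. This agrees with the four groups and four doses announced in C) Groups, so the duplicate letter does not signal a merged arm.

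**3. Look for a second key.** There is none. The only other C) is the subsection heading for Groups itself. Two one-letter corrections are possible: 0 mg becomes C, or 4.5 mg becomes C. Because A and B rise with dose, some readers will lean towards C for 4.5 mg. Others will take the last-listed arm to be D. The documents do not decide.

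**4. Look for any instruction that uses the letters.**

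- *Treatment.* Preparation and the later administrations are described by dose, with no reference to a letter.
- *Outcomes.* The primary outcome (PCA morphine over 72 hours) and the secondary scales are defined without reference to arms.
- *Analysis.* The planned overall tests ask whether the groups differ. Their result depends on which patients are grouped together and is unchanged if groups are renamed. With four arms the between-group degrees of freedom are 4 − 1 = 3 under either correction.

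**5. Ask what would happen if someone used the printed letters literally.** A grouping variable coded this way would have 3 levels with planned sizes 22 (A), 22 (B) and 22 + 22 = 44 (D), and 3 − 1 = 2 degrees of freedom. One level of double size, in a trial with four equal arms, would show up in the first tabulation. A literal use of the slip would therefore reveal itself.

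**The case for a change.** The best case for acting is that a public protocol should let an outside reader audit results against the arm definitions, and that the correction costs almost nothing. The two arms involved hold 44 of the 88 planned patients, the treatments cannot be told apart by sight, and the ambiguity falls on the control. The step 5 argument also has a limit: if records used four letters but a reader guessed wrongly which of C and D was the control, group sizes would give no warning.

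Part of this stands. The sentence is wrong as printed, the rest of the text does not repair it, and a results table showing letters without doses could not be decoded from this document. A misread letter in the text conversion cannot be wholly excluded, but nothing around the sentence looks damaged.

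The rest depends on records that the documents do not describe. They mention a table of random numbers and a pharmacist who dilutes the doses. They do not say that the letters served as the working code. The sentence may not be the working key at all: "Patients were randomized (by using a table of random numbers) to one of four groups" is in the past tense, and two references carry access dates in July 2024 under a title date of February 2020, so at least part of the text was edited late. That does not prove when the slip arose, but it weakens the inference from a printed letter to an allocation error. The figure of 44 out of 88 only restates that two of four equal arms are half the trial; it does not count records at risk.

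**Conclusion.** The slip is real, but it calls for no change to the plan. Four doses are printed with three letters, and the arms remain fully identified by the doses beside them. No treatment step, outcome definition or planned test relies on the letters, so carrying out the plan as written gives the same data and the same conclusions whichever D is the misprint. An analyst would label the arms by dose, which is also the natural scale for a dose-response question, and the ambiguity would disappear.

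This rests on two assumptions: that the pharmacist and the dataset can identify each patient's dose, which the Procedure requires in any case for the later administrations, and that results are reported with doses attached. Nothing in the documents contradicts either. The letter itself is an editorial matter, to be settled from the allocation record whenever the text is next touched.

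One neighbouring point is separate and is not judged here: C) Groups speaks of a single dose, while Procedure has the same dose given again at 24 and 48 hours. Those two statements need reconciling on their own account; they do not alter the conclusion about the letters.

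### The stated 80% power names neither a contrast nor a metric, and it does not cover separating neighbouring active doses, which choosing an optimum dose requires

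*Combined protocol and SAP*

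**What the plan says.** The Background gives the aim as "to determine the optimum dose of epidural morphine for the highest control of acute postoperative pain in geriatrics", and the title calls the trial a dose-response study. Section C randomises to four doses: 0, 1.5, 3 and 4.5 mg. The primary outcome, under Aim of the research, is PCA morphine use over 72 hours.

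Section D sizes the trial "considering a study power of 80% and a significance level of 0.05 to detect an effect size of 0.75". The test is one-"way ANOVA test/t-test", with no statement of which was used. The planning values are "the maximum total IV-PCA morphine consumption was 12 ± 16 mg while in healthy controls was 70 ± 35 mg", attributed jointly to three earlier studies. The result is 88 patients, 22 per group, after a 33% dropout allowance.

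The Statistical Analysis Plan offers ANOVA or Kruskal–Wallis across groups, with Bonferroni correction when several time points or tests are involved. It does not give the number of comparisons. No difference between active doses, no SD by dose, and no pairwise or trend contrast is specified anywhere.

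**The concern.** A four-arm trial that includes a 0 mg arm asks two things: whether epidural morphine reduces PCA use, and which active dose does so best. One planning contrast between a low-consumption group and a control group speaks at most to the first. The optimum dose depends also on differences among 1.5, 3 and 4.5 mg, and the 80% is not tied to any such difference.

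At stake is how the result is read. A four-arm test can be significant because of the 0 mg arm alone and so say nothing about the ranking of active doses. With 80% power printed and no contrast named, a reader could also take a non-significant comparison of two active doses as evidence that they work equally well.

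**Working it through.** **Inputs.** From section D: alpha 0.05 (two-sided assumed; the plan does not say), power 80%, effect size 0.75, 12 ± 16 and 70 ± 35 mg, 33% dropout, 22 per arm. Evaluable per arm: 22 × 0.67 = 14.7, taken as 15. Pooled SD: √((16² + 35²)/2) = 27.2 mg. Power is from the exact noncentral t or F distribution.

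**The plan's own figure.** A two-sided two-sample t-test at d = 0.75 and 80% power needs 29 per arm, or 58 for two arms. 58/0.67 = 86.6, so 87, and 88 as a multiple of four. Four-group ANOVA at f = 0.75 needs 6 per group, 24 in all and 36 after dropout, which does not match. The 88 is therefore consistent with a two-group total spread over four arms. The plan does not say this, and the results below do not depend on it.

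**If 0.75 is d for a pair of doses.** Noncentrality = 0.75 × √(n/2), which is 2.49 at n = 22 and 2.05 at n = 15.

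| Adjustment | 22 per arm | 15 per arm |
|---|---|---|
| None | 68% | 51% |
| Bonferroni, 3 active pairs | 50% | 33% |
| Bonferroni, all 6 pairs | 40% | 24% |

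**If 0.75 is f for the four-arm test.** Power is over 99.8% at 15 or 22 per arm. Now make the three active doses identical at 12 mg, with 0 mg at 70 mg. The SD of the means is 58 × √3/4 = 25.1 mg, f = 25.1/27.2 = 0.92, and power is above 99.9% at either size. The test is then almost certain to be significant with no difference among active doses.

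**The planning contrast itself.** d = (70 − 12)/27.2 = 2.13; power is above 99.9% at either size.

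**Active doses, scenario 1 (assumption): 12 mg is the highest active-arm mean and SD is 16.** Then 0.75 × 16 = 12 mg, the whole of that mean, so the other dose would need zero consumption. The difference detectable with 80% power is 13.8 mg (22 per arm) or 17.0 mg (15 per arm), both above 12 mg.

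**Active doses, scenario 2 (assumption): a linear fall from 70 mg at dose 0 to 12 mg at 4.5 mg, SD 27.2.** The step between adjacent doses is 58/3 = 19.3 mg.
- 1.5 v 4.5 mg: d = 38.7/27.2 = 1.42; power 99.6% (22) or 96% (15) unadjusted, 97% or 84% with Bonferroni for six pairs.
- Adjacent doses: d = 19.3/27.2 = 0.71; power 63% (22) or 47% (15) unadjusted.

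**Expected 95% CI half-width for a difference between two doses**, t × SD × √(2/n), with t = 2.018 (42 df) or 2.048 (28 df):

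| SD in both arms (mg) | 22 per arm | 15 per arm |
|---|---|---|
| 16 | ± 9.7 | ± 12.0 |
| 27.2 | ± 16.6 | ± 20.3 |
| 35 | ± 21.3 | ± 26.2 |

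These are unadjusted; multiplicity-adjusted intervals are wider. An SD of 16 around a mean of 12 implies skewed data, so all t and F figures are approximate.

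**The case against.** Several stronger readings are tempting, and the documents do not carry them.

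- **That the planning figures are morphine against none.** Section D speaks of healthy controls and does not say which of the three cited studies supplied which value. By title, one concerns binaural beats after knee replacement, one a nerve block in hip arthroplasty and one post-caesarean epidural morphine.
- **That 12 mg is a ceiling for every active arm.** The word maximum is ambiguous; 12 mg could be consumption at maximal effect. Scenario 2 follows from that reading, and there the widest active-dose comparison is well powered. So a reader cannot infer that the 80% is too high for every active-dose contrast.
- **That 0.75 must be d.** It may be f: means of 12, 41, 41 and 70 mg at SD 27.2 give f = (29/√2)/27.2 = 0.754. In that case 0.75 × 16 is not a pairwise effect.
- **That the trial's question concerns active doses only.** The 0 mg arm is part of the dose-response, and that part is amply powered at the planning values.
- **That non-significance will be reported as equal effect.** The plan does not say so; this is a risk that its wording leaves open.

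The half-widths are also conditional. If the SD falls with the mean (12 v 6 mg, SDs 16 and 8), they are about ± 7.8 or ± 9.6 mg.

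All of this stands as a limit on the point. It does not supply a powered contrast between neighbouring active doses: even the most favourable case examined gives 63% or 47%.

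**Conclusion.** The concern holds in limited form. The 80% fits neither reading at the planned size: a pairwise d of 0.75 has 68% (51% with 15 evaluable) before any correction, and a four-arm f of 0.75 has over 99.8%. No contrast between active doses is specified, and neighbouring doses fall short of 80% under every reading examined. The size of the shortfall depends on assumptions that the plan does not settle: what 12 mg represents, which SD applies, how consumption falls with dose, and how many comparisons are corrected for. The pairwise and four-arm figures need only section D's numbers and a two-sided alpha. The 12 mg equivalence and the linear case each need the assumption stated with them. This should be corrected, but it does not invalidate the design.

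**What to change.** In section D, name the contrast and the metric to which the 80% applies, and restate the power for active-dose comparisons as tabulated above. Add the expected 95% CI half-widths as a range over the stated SDs (± 9.7 to ± 21.3 mg at 22 per arm; ± 12.0 to ± 26.2 mg at 15), noting that skewness makes them approximate.

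In the aim and the Statistical Analysis Plan, state that:
- differences between active doses will be reported as estimates with multiplicity-adjusted intervals, consistent with the planned Bonferroni correction, by a method valid for skewed data, and with the number of comparisons given;
- a non-significant difference will not be reported as equal effect;
- a significant four-arm test alone will not be used to call one active dose best on PCA use.

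The cost is wording. No extra patients are needed. The downside is a less favourable stated power and a narrower claim.

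### 88 patients is the two-group t-test total for d = 0.75 after 33% dropout; as four groups of 22 it follows from neither reading of the stated effect size

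*Combined protocol and SAP*

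**What the plan says.** Section D (Sample Size Calculation) describes a G*Power calculation with "a study power of 80% and a significance level of 0.05 to detect an effect size of 0.75". The test is given as a one-"way ANOVA test/t-test", so two different procedures are named. The planning values are that the "maximum total IV-PCA morphine consumption was 12 ± 16 mg while in healthy controls was 70 ± 35 mg". The conclusion is that "the estimated minimum required sample size, after assuming 33% dropouts, will be 88 patients (22 patients in each group").

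Section C (Groups) sets the design: "Patients were randomized (by using a table of random numbers) to one of four groups". The Background gives the aim as "to determine the optimum dose of epidural morphine for the highest control of acute postoperative pain". The Statistical Analysis Plan says that significant Kruskal–Wallis results will be "Bonferroni corrected when various time points are investigated and when multiple tests are applied".

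The section does not state the effect-size metric, the sidedness, the comparison being powered, the number evaluable before dropout, or how 0.75 was obtained from the planning values.

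**The concern.** An effect size of 0.75 means very different things in the two procedures named. As d it is a difference of 0.75 SD between two groups. As f in a four-group ANOVA it is a between-group spread of 0.75 SD, which is very large. The sample sizes differ several-fold, so a reader has to know which was used before 88 can be checked.

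The aim makes this more than a labelling question. Choosing an optimum among 0, 1.5, 3 and 4.5 mg needs comparisons between doses as well as an overall test. If the 80% claim is taken to cover those comparisons and does not, a non-significant difference between two doses could be misread as showing that they are equally good.

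**Working it through.** **Inputs, all from section D unless noted.** Alpha 0.05; power 80%; effect size 0.75; dropout 33%; four equal groups (section C); planning means and SDs 12 (16) and 70 (35) mg. Sidedness is not stated, so two-sided is assumed. Power is exact: noncentral t with 2n − 2 df and noncentrality d√(n/2) for two groups; noncentral F with noncentrality f²N for the ANOVA. Dropout is applied as n/(1 − 0.33).

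**Reading 1: 0.75 is d, two-sided t-test.**
- n = 28 per group gives power 0.787; n = 29 gives 0.801. So 29 per group are needed.
- 29/0.67 = 43.3, rounded up to 44 per group.
- Two groups: 2 × 44 = **88**, exactly the stated total.
- Four groups: 4 × 44 = **176**. The stated 22 per group is half of 44.
- Check: 88 × 0.67 = 59.0 completers, against the 2 × 29 = 58 needed by two groups.

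**Reading 2: 0.75 is f, one-way ANOVA, k = 4.**
- N = 20 gives power 0.701; N = 24 gives 0.807. So 24 completers are needed.
- 24/0.67 = 35.8, so **36** enrolled, not 88.

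**Other routes from 0.75 to a four-group total after dropout.**

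| Route | Evaluable | After 33% dropout |
|---|---|---|
| One-sided t-test, d = 0.75 | 23 per group | 140 |
| Two-sided t-test, inflated by × 1.33 | 29 per group | 156 |
| Two-sided normal approximation | 28 per group | 168 |
| ANOVA, f = d/2 = 0.375 | 84 in total | 128 |
| ANOVA, extreme groups 0.75 SD apart (f = 0.265 to 0.280) | 160 to 144 in total | 240 to 216 |

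None gives 88. A one-sided normal approximation gives 22 per group, and 4 × 22 = 88, but only with no dropout allowance. That contradicts the stated 33%, and the exact one-sided t-test needs 23.

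**Do the planning values settle the metric?**
- Root-mean-square SD = √((16² + 35²)/2) = 27.2 mg.
- d = (70 − 12)/27.2 = 2.13, far from 0.75. At d = 2.13, 5 per group would give 80% power.
- If the other two groups sit at the midpoint (the minimum-variability pattern), f = 2.13 × √(1/8) = 0.754.

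The planning values therefore point towards f, while the total points towards a two-group calculation on d.

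**What 22 per group delivers.** 22 × 0.67 = 14.7, so about 15 per group are evaluable. For a two-sided t-test between two doses:

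| Alpha | Power for 0.75 SD, n = 22 | Power for 0.75 SD, n = 15 | Detectable with 80% power, n = 15 | In mg at SD 16 / SD 35 |
|---|---|---|---|---|
| 0.05 | 0.68 | 0.51 | 1.06 SD | 17 / 37 |
| 0.05/3 (each dose v 0 mg) | 0.50 | 0.33 | 1.25 SD | 20 / 44 |
| 0.05/6 (all pairs) | 0.40 | 0.24 | 1.36 SD | 22 / 48 |

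At 14 per group the unadjusted power is 0.48. For the overall ANOVA with 60 completers, power at f = 0.75 is 0.999, and the f detectable with 80% power is 0.44 (0.441 to three places).

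**The case against.** The strongest reply is that the plan's own figures favour the f reading. They give d = 2.13 rather than 0.75, and ANOVA is the first test named. On that reading the overall test has power 0.999. For the one contrast that the plan quantifies, pairwise power at 15 per group is also above 0.99, even with Bonferroni for six pairs. This stands: underpowering of the overall test, or of a difference as large as 58 mg, is not shown. It does not rescue 88, because f = 0.75 leads to 36 enrolled, and it gives no assurance about smaller differences between active doses.

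It can also be said that the f match is fragile. The value 0.754 depends on the SD of 27.2 and the midpoint pattern. With the same SD, an evenly spaced pattern gives 0.79, and one group at 70 with three at 12 gives 0.92; at SD 35 the three patterns give 0.59 to 0.72. That is fair. The f match is suggestive only, as is the match of 88 to a two-group total.

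The Bonferroni sentence is written about Kruskal–Wallis results, and the plan defines no family of dose pairs. The three- and six-comparison figures are therefore assumptions about how its multiple-tests clause would apply to dose comparisons. They are shown beside the unadjusted ones, and the shortfall on the d reading exists without them.

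Finally, the plan specifies no pairwise t-test and falls back on Kruskal–Wallis if normality is rejected. The t-test figures are therefore a guide to pairwise power under normality, not a prediction for the rank test.

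**Conclusion.** The concern holds. On neither reading of 0.75 is 22 per group the size that the stated inputs require for four arms: the d reading needs 44 per group (176 in total) and the f reading needs 9 per group (36 in total). The exact agreement of 88 with a two-group total suggests that such a total was divided over four arms, but this is an inference; the documents do not show the step.

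The firm finding is that the only sample-size justification for the primary outcome cannot be reproduced for the actual design and does not say what is powered. Calling 22 half of the requirement applies to the d reading only, and assumes a two-sided test and dropout applied by division by 0.67. If f was meant, the overall test has ample power, 88 has no stated basis, and the 80% claim says nothing about differences between doses. Because the aim is to choose a dose, this needs correcting before the 80% figure is relied on.

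**What to change.** Keep 88 and correct section D. Name one test, one effect measure (d or f), the sidedness and the comparison powered, and give the evaluable number before dropout. Replace the power sentence with what the design delivers, for example:

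> With 88 enrolled (22 per group) and 33% dropout, about 15 per group are evaluable. This gives 80% power at alpha 0.05 for f = 0.44 in the four-group one-way ANOVA. For a two-sided pairwise t-test, the difference detectable with 80% power is 1.06 SD unadjusted, 1.25 SD with Bonferroni for three comparisons and 1.36 SD for six. Power for a 0.75 SD pairwise difference is 51%, 33% and 24% respectively.

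Keep only the multiplicity case that matches the comparisons finally specified. If a value in mg is given, show the range over the planning SDs (1.06 SD is about 17 mg at SD 16 and 37 mg at SD 35). If 0.75 was meant as f, say so, state that 24 completers suffice for the overall test, and give the reason for enrolling 88. On either reading, do not claim 80% power for a 0.75 SD pairwise difference.

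The cost is wording only, with no extra patients; the downside is a less favourable stated pairwise power. Holding 80% for a 0.75 SD pairwise difference in four arms would need 176 enrolled before any multiplicity correction, which is not proposed here.
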